However, not all high-risk patients are candidates for the ICD for a variety of reasons [2-4]. These are: transient nature of the high-risk for SCD; patients who do not meet current guideline indications for an ICD; high-risk cardiac patients who had previously received an ICD but had it removed because of complications or malfunction; patients who refuse an ICD; age-related factors; and a variety of other medical and ethical considerations [5].

The Wearable Cardioverter-Defibrillator (WCD) LifeVest by ZOLL, Pittsburgh, PA, USA is an external defibrillator, guided by an algorithm to detect ventricular tachyarrhythmic events and gives the patient's physician time to assess the long-term arrhythmic risk in cases when the risk of life-threatening arrhythmias may only be temporary and to make appropriate plans.

4.1 Primary study objectives

1. **Appropriate shocks** as measured by shocks delivered for adjudicated sustained ventricular tachycardia (VT) or ventricular fibrillation (VF) episodes.
2. **Inappropriate shocks** as measured by shocks delivered for all episodes that are not adjudicated sustained VT or VF episodes.

The frequency and rate of appropriate and inappropriate shocks will be measured. The risk of receiving an inappropriate shock will be analyzed. The risk of not receiving appropriate shocks when necessary will also be analyzed.

4.2 Secondary study objectives

1. Overall survival as measured by the ratio of the number of patients that are alive at the end of the use of the WCD to the total population of patients prescribed the LifeVest.
2. Quality of life relative to health state as measured through the administration of a patient quality of life survey. This survey has been used previously in a published study of patient quality of life.

LifeVest has been recently approved for reimbursement by the HAS. LifeVest has obtained coverage for 4 indications: (i) implantable cardiac defibrillator (ICD) removal due to cardiac device infections, (ii) a bridge to heart transplantation, (iii) in the early post-MI period with left ventricular (LV) dysfunction (LVEF <30 %), (iv) and a recent coronary revascularization with LV dysfunction (LVEF < 30 %). There is no current comparator to LifeVest. In France, patients at high risk for sudden cardiac arrest and waiting for heart transplant or ICD are hospitalized or discharged home without any particular ECG monitoring. LifeVest has been demonstrated to automatically detect and terminate rapid ventricular

arrhythmias. Introduction of LifeVest into the current patient management would definitely improve the clinical outcomes and benefit the patients with temporary risk of SCD. The use of LifeVest was shown to be effective in protecting patients against SCD in the United States. However, the clinical impact of using LifeVest in France remains unassessed. Therefore, this post-market study in France will provide efficacy and safety data for the reimbursement dossier renewal before September 2018.

5. Sample size and Power

This study is a post-inscription study designed to describe all patients treated by LifeVest in a comprehensive way. Thus this study will be proposed to all patients receiving LifeVest.

No sample size calculation has been planned. All patients accepting to participate will be included.

The LifeVest device is commercialized in France since approximatively 3 years, the number of subjects has been estimated based on the sales and the foreseen participation rate.

It was estimated that approximately 1,700 patients will receive LifeVest in clinical routine between May 2015 and April 2018 (300 patients first year, 520 patients second year and 880 patients third year of marketing) in France. After obtaining all regulatory approvals, the study started in August 2016.

Between August 2016 and April 2018, 1,110 patients were expected to receive LifeVest in clinical routine. Considering a participation rate of 50 % related to centers participating in the study and consent given, around 550 patients were considered to participate in this study.

Due to an observed recruitment rate exceeding the initial expectations, the recruitment goal was reached prematurely with an estimated enrollment of about 1,200 patients until 31st March 2018. After the end of recruitment, follow-up of patients is planned until 31st march 2019 (LPLV).

According to most recent data from literature, the frequency of ventricular tachyarrhythmic events with shock delivery within the spectrum of indications for the LifeVest device and within the associated wearing periods was estimated between 1% and 5% [6]. In this present study, a population of 550 patients was expected as primary assumption, allowing to observe a shock delivery rate ranging between 1%-5% with an absolute precision below 2% (0.8 for 1% and 1.8 for 5%). This sample size was considered to be statistically sufficient to answer the pre-defined research questions, however, the expected final population in the study of about 1,200 patients will increase the level of precision.

6. Analysis populations

6.1 Intention to treat population (ITT)

ITT analysis in general includes every subject who is randomised according to randomised treatment assignment [7]. Since this is an observational study without randomisation, the equivalent, fundamental claim of "intention-to-treat" is the fulfilment of in- and exclusion criteria after giving informed consent on the use of medical data.

All consenting patients with a routinely prescribed WCD in study participating centers will be evaluated, regardless of the length of WCD wearing. This may include patients who have already completed use of LifeVest before start of the study in the corresponding study site.

Patients with missing outcome data are not considered in the outcome analysis [8].

The retrospective cohort of patients will be analyzed separately compared to prospectively included study patients for any variables that are not available for both cohorts, such as the patient survey.

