5.2 Subjects

Study population will consist of patients at high risk for SCD and receiving LifeVest as a bridge therapy to heart transplantation, to ICD or to improvement of LV function.

5.2.1 Inclusion criteria for subject selection.

- Patients receiving a LifeVest prescription in clinical routine for the following indications:
 - a) implantable cardiac defibrillator (ICD) removal due to cardiac device infections,
 - b) a bridge to heart transplantation,
 - c) in the early post-MI period with left ventricular (LV) dysfunction (LVEF <30%),
 - d) a recent coronary revascularization with LV dysfunction (LVEF < 30%).
- Patients who have given their consent to participate.

This includes also those patients who have already completed use of LifeVest before start of the study in the corresponding study site (retrospective inclusion).

5.2.2 Exclusion criteria for subject selection.

There are no exclusion criteria for this study other than if the patient does not provide informed consent to participate. All patients prescribed a LifeVest will be invited to participate. All patients that were previously prescribed a LifeVest before the start of this study will also be invited to participate by allowing access to their retrospective medical information.

5.2.3 Criteria and procedures for subject withdrawal or discontinuation.

A low rate of lost-to-follow up is expected since the LifeVest is rented to patients and should be returned to ZOLL by the end of the prescription. In case a patient is lost to follow up, the CepiDC a French database for automated coding of causes of death, will be interrogated to report if the patient is dead or alive, and if dead the cause of death.

All patients enrolled into the study can withdraw at any time regardless of the reason. Patients may withdraw consent for use of data and exit the study at any time without prejudice to further treatment.

Patients who have given consent to participate in the study but had the WCD for less than 8 days will be evaluated separately, but not withdrawn.

5.2.4 Participating centers and point of enrolment:

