5.4 Monitoring plan

Authorized, qualified representatives of the sponsor will accomplish on-site monitoring during the study. The accuracy and completeness of core CRF data of a sufficient number of patients will be checked on site against source documents. Details will be given in a risk based monitoring plan.

Quality management will assure that medical data are subject of continuous plausibility checks and data cleaning. The primary outcome parameters consist of follow-up and arrhythmic event raw data which are directly transmitted in clinical routine from the WCD device to a central database to which the treating physician has access via an internet platform enabling him to review any potential arrhythmic event

detected by the device. These data are not modified by human interactions, thus being *per se* valid and do not require source data verification.

6. Statistical considerations and methods

This is a nonrandomized, multicenter observational study. All consecutive LifeVest patients will be asked to participate. Demographic data will be reported on all consenting patients. Thus, all patients in this study will receive LifeVest treatment. Descriptive statistics will be used to report major clinical characteristics of consenting patients, and incidence and frequency of appropriate and inappropriate shocks.

For the overall survival rate calculation, the population of reference will correspond to the total number of patients enrolled who were prescribed the LifeVest.

Standard methods will be used to calculate adjusted survival rates. Kaplan Meier survival curves will be used to report total mortality and wear time. The time to event and census are defined here after.

All reasons for therapy discontinuation will be reported in tabular form.

Event	Decision	Event date or census date
Occurrence of the event	Not censored	Date of the event occurrence
No event and patient followed until the study end	Censored	Date of WCD withdrawal
Lost-to-follow-up	Censored	Date of the last visit or last contact

It is common to use a significance threshold of 5%. This will be applied in this study.

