7.2 Dataset for interim analysis

An interim analysis is planned for reimbursement dossier renewal latest in September 2018. For this purpose a dataset for interim analyses will be generated at a specific point in time defined by the sponsor. The dataset for interim analysis is a data snapshot and will partially consist of uncleaned data because data documentation and cleaning are ongoing at this point in time.

8. General methodology

Continuous variables will be summarized as means (standard deviations [SDs]), quartiles (25 %, 50 % and 75 %), and minimum and maximum value. The number and percentage of patients in each category will be presented for nominal variables. For graphical representation distribution plots, histograms, boxplots and bar charts will be used, as appropriate.

Comparisons of continuous variables will be performed using the Student’s t-test and if assumptions are not met Wilcoxon rank-sum test, and comparisons of nominal variables will be performed using the Pearson’s chi-square test or Fisher’s exact test, as appropriate.

For time-to-event data, the Cox proportional hazards model will be used unless specified otherwise. Survival estimates will be illustrated in Kaplan-Meier plots.

For comparing groups with respect to binary outcomes, logistic regression or analysis of covariance (ANCOVA) will be used as specified.

Statistical comparisons will be performed using two-sided significance tests with alpha=0.05 unless otherwise noted.

9. Demographics and characteristics of ITT population

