- The risk of receiving an inappropriate shock, calculated as number of inappropriate shocks/ non VT/VF events

11. Secondary analysis on ITT population

Overall survival as measured by the ratio of the number of patients that are alive at the end of the use of the WCD compared to the total ITT population.

Survival analysis using Kaplan-Meier curves and cox proportional hazard models will be performed to identify impacts on survival and the occurrence of WCD events will be displayed in tables in the following subgroups :

- indication for the WCD,
- medical history, and
- disease etiology: heart failure according to ESC guidelines
 - no HF (LV-EF $\geq 50\%$)

- intermediate HF (LV-EF $\geq 40 - < 50\%$)
- HF (LV-EF $< 40\%$)

12. Efficacy and safety analysis on ITT population

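### Does the SAP's exclusion of patients with missing outcomes leave the overall survival denominator undecided?

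*Combined protocol and SAP*

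**What the plan says.** The denominator for overall survival appears in four places.

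- Protocol 4.1 and SAP 4.2 (secondary objectives) relate patients alive at the end of WCD use "to the total population of patients prescribed the LifeVest" (wording of SAP 4.2).
- Protocol 6 addresses the survival rate by name: "the population of reference will correspond to the total number of patients enrolled who were prescribed the LifeVest".
- SAP 11 takes the number "alive at the end of the use of the WCD compared to the total ITT population".

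SAP 6.1 defines that ITT population as all consenting patients with a routinely prescribed WCD, whatever the wearing time. It then adds a general sentence, tied to no particular outcome: "Patients with missing outcome data are not considered in the outcome analysis". SAP 15 rules out imputation.

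For the Kaplan-Meier analysis, the table in protocol 6 censors patients lost to follow-up at "Date of the last visit or last contact". Those in the row "No event and patient followed until the study end" are censored at WCD withdrawal.

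On loss to follow-up, protocol 5.2.3 says "A low rate of lost-to-follow up is expected", because the device is rented and should be returned. It adds that the French cause-of-death database (CepiDC) will be queried for anyone lost.

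**The concern.** Read side by side, SAP 6.1 and SAP 11 give different ratios whenever someone's vital status is unknown. Under SAP 11 that patient stays in the denominator. With no imputation the patient cannot enter the numerator, and so counts in effect as not alive. Under SAP 6.1 the patient leaves both. If the SAP 6.1 sentence is carried over to Kaplan-Meier and Cox as well, it would remove patients whom the protocol 6 table keeps and censors.

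Overall survival is a named secondary objective, and the study is meant to support a reimbursement renewal. With about 1,200 patients the sampling error is small, so a few patients of unknown status could move the ratio by more than its confidence half-width.

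There is also a question about the interim. SAP 7.2 says "An interim analysis is planned for reimbursement dossier renewal latest in September 2018". A patient still wearing the device at that snapshot has no end-of-use status, and the protocol 6 table gives no censoring date for that case.

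**Working it through.** **The plan's own figure.** The only precision statement concerns the shock rate (protocol 6.1, SAP 5): 0.8 points at 1% and 1.8 points at 5% with 550 patients. The half-width 1.96 × √(p(1−p)/N) gives 1.96 × √(0.01 × 0.99/550) = 0.83 points and 1.96 × √(0.05 × 0.95/550) = 1.82 points, so it reproduces. No such figure is given for survival.

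**Inputs for the ratio.** N = 1,200 is the expected enrolment in SAP 5. The documents give neither a death count D nor a number U of unknown status, so both are assumed: D = 30 as the central case, with 12 and 60 as the range, and U from 0 to 24 (0% to 2%).

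**Formulas.** Patients known alive: A = N − D − U. Total-ITT rule: A/N. Exclusion rule: A/(N − U). Gap: A × U / (N × (N − U)).

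| U (D = 30) | Total ITT | Exclusion | Gap (points) |
|---|---|---|---|
| 0 | 1,170/1,200 = 97.50% | 1,170/1,200 = 97.50% | 0 |
| 6 (0.5%) | 1,164/1,200 = 97.00% | 1,164/1,194 = 97.49% | 0.49 |
| 12 (1%) | 1,158/1,200 = 96.50% | 1,158/1,188 = 97.47% | 0.97 |
| 24 (2%) | 1,146/1,200 = 95.50% | 1,146/1,176 = 97.45% | 1.95 |

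The gap is roughly the survival proportion times the unknown share, hence about 1 point per 1% unknown.

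**Against sampling error.** With D = 30 the half-width is 1.96 × √(0.025 × 0.975/1,200) = 0.88 points. The gap is 0.81 at U = 10 and 0.89 at U = 11, so it passes the half-width at 11 patients (0.9%). With D = 12 (half-width 0.56) this happens at U = 7 (0.6%); with D = 60 (half-width 1.23) at U = 16 (1.3%).

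**Kaplan-Meier.** A simulation assumed exponential wear with a 3-month mean, a death hazard of 0.00855 per month (2.5% dying during use) and loss at a uniform point within use. With 2% lost, mortality when they are censored against excluded is 2.51% and 2.54% at 3 months, and 4.97% and 5.02% at 6 months. With 1% lost it is 2.52% and 2.54%, then 4.99% and 5.01%. The choice is worth about 0.05 points at most.

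**Which text governs.** Four statements specific to this endpoint use the total population. The only text on the other side is one general sentence that names no endpoint. For Kaplan-Meier and Cox, a lost patient contributes follow-up time and a censoring status. That is usable time-to-event data and need not count as a missing outcome, so the SAP 6.1 sentence and the protocol 6 table can both be followed.

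**How many unknowns to expect.** The endpoint is status at the end of use, when the device should be returned and the reason for stopping, including death, is recorded (protocol 5.3.1.4, SAP 9.2). SAP 5 ends recruitment on 31 March 2018 and follow-up on 31 March 2019, 12 months later, against a mean wear of about 3 months (protocol 5.2.8). Lost patients are then looked up in CepiDC.

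**The case for a change.** The best case for a change is that SAP 6.1 is the one rule written for missing outcomes and that it exempts nothing. Protocol 6 fixes the denominator but is silent on the numerator, and the SAP has no censoring table of its own. Two programmers could therefore produce different ratios for a named secondary objective and each cite the SAP. Two or three sentences in SAP 11 would settle it without new data.

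Part of this stands. No sentence says how a patient still unknown after the CepiDC query is counted, and the arithmetic above is correct for the rates assumed.

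The rest is weaker. The documents do point to a denominator, so the claim that nothing governs fails. The Kaplan-Meier conflict arises only if SAP 6.1 is stretched to patients for whom protocol 6 gives an explicit rule. Making known-status patients the main denominator would replace the one written in four places with another that is no less debatable: the total-ITT ratio errs towards lower survival, while the known-status ratio assumes that unknown patients fared like the others.

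The interim point is conditional. SAP 7.2 does not say that survival will be reported at the snapshot, and the protocol 6 row on event-free patients is worded for the end of the study. If survival were reported then, censoring current wearers at the snapshot date is standard practice.

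**Conclusion.** The concern points to a missing detail that analysts fill sensibly, and the plan need not change. The total enrolled population is the documented denominator for the survival ratio, and lost patients are censored in the Kaplan-Meier analysis. The open detail is the handling of patients whose vital status is never established. It costs about 1 point of the crude ratio per 1% of such patients, nothing if there are none, and about 0.05 points at most on the Kaplan-Meier estimates with 1% to 2% lost.

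These sizes rest on assumed death and unknown rates, since the documents give neither. Device return, the CepiDC query and a year of follow-up after recruitment all point to few unknowns. No test, threshold or decision in the documents turns on the ratio. An ordinary report would state how many patients had unknown status, and a reader could then compute the ratio on either basis. The conclusion would weaken only if the unknown share at database closure proved well above the low rate the protocol expects.

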6.2 On-treatment population

Patients who have worn WCD for at least 8 days (i.e. longer than 1 week) will be evaluated separately in an “on-treatment” efficacy analysis, because it is assumed from clinical experience that the WCD wearing time will only be long enough for those patients to reliably compare their long-term outcome in a cohort of patients who have had the WCD for several months (even six or more months in some indications).

7. Analysis datasets

7.1 Final dataset

Dataset at time of study database closure (= after date of last visit and end of data cleaning = date of end of study EOS). No further changes of clinical data will be possible, neither by sites nor by CROs.

7.2 Dataset for interim analysis

An interim analysis is planned for reimbursement dossier renewal latest in September 2018. For this purpose a dataset for interim analyses will be generated at a specific point in time defined by the sponsor. The dataset for interim analysis is a data snapshot and will partially consist of uncleaned data because data documentation and cleaning are ongoing at this point in time.

8. General methodology

Continuous variables will be summarized as means (standard deviations [SDs]), quartiles (25 %, 50 % and 75 %), and minimum and maximum value. The number and percentage of patients in each category will be presented for nominal variables. For graphical representation distribution plots, histograms, boxplots and bar charts will be used, as appropriate.

Comparisons of continuous variables will be performed using the Student’s t-test and if assumptions are not met Wilcoxon rank-sum test, and comparisons of nominal variables will be performed using the Pearson’s chi-square test or Fisher’s exact test, as appropriate.

For time-to-event data, the Cox proportional hazards model will be used unless specified otherwise. Survival estimates will be illustrated in Kaplan-Meier plots.

For comparing groups with respect to binary outcomes, logistic regression or analysis of covariance (ANCOVA) will be used as specified.

Statistical comparisons will be performed using two-sided significance tests with alpha=0.05 unless otherwise noted.

9. Demographics and characteristics of ITT population

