5.1 General

5.1.1 Description of investigation

France post marketing protocol is an observational study of patients with a prescribed WCD during the time of risk assessment for future potential ICD therapy. Patients who are prescribed a WCD will be asked to participate in the prospective cohort of the study. Patients who have already completed use of LifeVest before start of the study in the corresponding study site can also be asked to consent for use of their clinical data to be included in the retrospective cohort of the study. The retrospective cohort of patients will be analysed separately compared to prospectively included study patients for any variables that are not available for both cohorts, such as the patient survey. Mean WCD wearing time is anticipated to be three months. However, some indications for wearing the WCD may be longer (up to 6 months) or shorter (only one month). For patients who are listed for heart transplantation, the wearing time is scheduled until heart transplantation is performed, or an ICD will be implanted.

5.1.2 Description of the measures to be taken to minimize or avoid bias, including randomization and blinding/masking

There is no randomization of patients enrolled into the study. All consenting patients with a routinely prescribed WCD in the study participating centers will be evaluated, regardless of the length of WCD wearing, including patients who have already completed use of LifeVest before start of the study in the corresponding study site.

The selection bias is limited by the protocol comprehensiveness. There will be no selection, the study will be proposed to all patients receiving LifeVest. In addition, all centres performing implantation of the device will be asked to participate. "Non-participants" will be described.

The attrition bias is also limited (non-existent) as at the end of LifeVest utilization, all material provided to the patient should be returned systematically. Furthermore, the patients follow- up is completely identical to the routine clinical practice. This means that we don't expect to have any difference between the data collected retrospectively and those collected prospectively. However, only patients included prospectively will be asked to complete the quality of life questionnaire.

The prospective cohort of patients will be analysed separately for variables not available for the patients in the retrospective cohort, such as the patient survey.

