12.2 Secondary parameters

- Analysis of primary outcome parameters (section 12.1) in sub-groups according to their clinical profile at baseline:
 - Age:
 - < 40 years
 - $\geq 40 - < 65$ years
 - $\geq 65 - < 75$ years
 - ≥ 75 years
 - Gender
 - Indication of WCD:
 - implantable cardiac defibrillator (ICD) removal due to cardiac device infections,
 - a bridge to heart transplantation,
 - in the early post-MI period with left ventricular (LV) dysfunction (LVEF $< 30\%$),
 - a recent coronary revascularization with LV dysfunction (LVEF $< 30\%$).
 - Type of inherited arrhythmia syndrome:
 - Long-QT syndrome (LQTS)
 - Brugada syndrome
 - Catecholaminergic polymorphous ventricular tachycardia (CPVT)

- Arrhythmogenic right ventricular cardiomyopathy
- Other
- Unknown

In addition the following parameters will be analysed in the mentioned subgroups:

- Cause of death (as assessed by CEC)
- Hospitalization
- Type of SAE

LV-EF at baseline and at time of WCD end of use

13. On-treatment efficacy analysis

For on-treatment efficacy analysis, tables on baseline characteristics and outcome will be shown comparing patient group on-treatment to not on-treatment (for definitions refer to 6.3).

14. Analysis of WCD usage on ITT population

Analysis of usage patterns will be done by:

- Description of WCD wearing profile:
 - Average prescription period
 - Average wearing period (date of activation to date of end of use)
 - Average wearing period by gender
 - Description and analysis of compliance of WCD wearing: WCD device in use during wearing period (days in use / number of days of wearing period) Average daily WCD usage (hours)
- Regression model/ANOVA evaluating factors influencing the non-compliance of patients with prescribed WCD (age, gender, neurologic function, co-morbidities etc.)
- Distribution of reasons for end of WCD usage
- Kaplan-Meier curves for time to end of WCD usage.

15. Missing values

Missing data will not be replaced by any algorithm.

16. Applied software

R (version 3.3.3 or later)

17. Literature

- 1) Myerburg RJ. Sudden cardiac death: exploring the limits of our knowledge. *J Cardiovasc Electrophysiol* 2001; 12:369-81.

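### SAP section 8 should name Welch's rather than Student's t-test, because Student and its Wilcoxon fallback can both miss the 5% level when groups differ in both size and spread

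*Combined protocol and SAP*

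**What the plan says.** SAP section 8 (General methodology) sets one rule for comparing continuous variables: Student's "t-test and if assumptions are not met Wilcoxon rank-sum test". Comparisons are "two-sided significance tests with alpha=0.05 unless otherwise noted". The section does not say whether variances are pooled, which assumptions are checked, or how. The same section reports continuous variables as means with SDs and also as quartiles.

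The clearest two-group use is SAP section 13, where "tables on baseline characteristics and outcome will be shown comparing patient group on-treatment to not on-treatment". The split comes from SAP section 6.2: "Patients who have worn WCD for at least 8 days (i.e. longer than 1 week) will be evaluated separately". Neither section gives the expected group sizes or lists the variables in the tables.

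On scale, SAP section 5 says that "the expected final population in the study of about 1,200 patients will increase the level of precision", and protocol section 5.1.1 says "Mean WCD wearing time is anticipated to be three months".

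**The concern.** Student's t-test estimates one common variance, and the larger group dominates that estimate. If the smaller group is the more variable one, the standard error is too small and the test rejects too often. If it is the less variable one, the test rejects too rarely. Equal variance is an assumption of Student's test, so a detected violation sends the analysis to Wilcoxon. Wilcoxon does not compare means, and when centres are equal but spreads differ its rejection rate also moves away from 5%. The fallback therefore reduces the problem without removing it.

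Both conditions are plausible for the section 13 tables. With a mean wear of about three months, few patients may fall below 8 days, although no split is stated. If average daily use appears in those tables (the SAP does not say), it would rest on at most 7 days per patient in one group and often on months in the other. Other things equal, the smaller group would then be the noisier one. At stake is whether p-values in these tables can be taken at the stated 5% level.

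**Working it through.** **The plan's own figure.** The only design figure is the precision of the shock rate with 550 patients (SAP section 5). It reproduces: 1.96 × √(0.01 × 0.99/550) = 0.83 points and 1.96 × √(0.05 × 0.95/550) = 1.82 points, against 0.8 and 1.8 stated. It does not bear on the group comparisons, for which the plan gives no figure.

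**Inputs.** Total of 1,200 (SAP section 5) and two-sided 5% (SAP section 8) are from the documents. Assumed: 60, 120 or 240 patients in the smaller group (5%, 10%, 20%), SD ratio r (smaller group to larger) from 0.5 to 2, equal true means, normal data.

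**Large-sample formula for Student.** With the larger group's SD set to 1 and sizes n₁ (larger) and n₂ (smaller):
- squared standard error used by Student: [((n₁−1) + (n₂−1)r²)/(n₁+n₂−2)] × (1/n₁ + 1/n₂)
- true squared standard error: 1/n₁ + r²/n₂
- type I error: 2 × [1 − Φ(1.96 × √(used/true))]

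For 1,140 versus 60 with r = 2:
- used = (1,139 + 59 × 4)/1,198 × (1/1,140 + 1/60) = 1.1477 × 0.017544 = 0.02014
- true = 1/1,140 + 4/60 = 0.06754
- √(0.02014/0.06754) = 0.546, and 1.96 × 0.546 = 1.070, so the type I error is about 28.5%.

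**Simulation, 10,000 runs per setting.** Type I error in %, for smaller groups of 60 / 120 / 240:

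| SD ratio | Student | Wilcoxon |
|---|---|---|
| 0.5 | <0.1 / 0.05 / 0.4 | 0.3 / 0.6 / 1.6 |
| 0.67 | 0.6 / 0.7 / 1.4 | 1.6 / 1.8 / 2.7 |
| 1 | 4.9 / 5.1 / 4.9 | 5.0 / 5.2 / 4.9 |
| 1.5 | 16.8 / 15.8 / 12.2 | 9.6 / 9.1 / 8.4 |
| 2 | 28.6 / 23.7 / 18.1 | 13.1 / 11.9 / 11.2 |

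Welch stayed between 4.6% and 5.3% in every one of these settings. The row for ratio 1 shows that unequal size alone does no harm. With 600 per group and ratio 0.5 or 2, Student was 5.0–5.2% and Wilcoxon 6.3–6.4%, so the large errors need both imbalances.

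**Milder spread differences** (smaller group 60, 100 or 200). Ratio 1.1: Student 6.3–7.3%, Wilcoxon 5.7–6.3%. Ratio 1.2: Student 8.0–9.5%, Wilcoxon 6.5–7.1%.

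**The path the plan describes.** At these sizes a formal variance check would almost always detect a ratio of 1.5 to 2, so the planned procedure would run Wilcoxon. Its error as a comparison of means is then about 8–13%. At ratios of 0.5 to 0.67 it falls to roughly 0.3–2.7%.

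**Strong skew, identical distributions** (lognormal, log-scale SD 0.8). With 60 and 120 in the smaller group, Welch gives 7.5% and 6.2%, Student 5.0% and 5.2%, and Wilcoxon 5.1% and 5.4%. A separate lognormal run gave Welch 8.3% with 60 and 7.1% with 100.

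**The case against.** The strongest reply is that the harm rests on quantities that the documents do not give. No group sizes or SDs are stated, and no baseline variable in SAP section 9.1 is shown to differ in spread between the groups. That stands: the figures are conditional, and with mild differences in spread the distortion is small.

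The larger Student figures also apply only if a variance violation goes unnoticed, because section 8 says to leave Student's test when its assumptions fail. That stands too. For large differences in spread the Wilcoxon figures are the relevant ones, unless the assumption check, which the SAP leaves undescribed, is not made.

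Wilcoxon keeps its level for its own null hypothesis of identical distributions, and section 8 reports quartiles beside which a rank test sits naturally. This is correct. The difficulty arises only when its p-value is read as a statement about means.

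A reader might extend the point to men versus women. SAP section 14 does list "Average wearing period by gender", but under description of the wearing profile, with no test attached, and no document suggests how the sexes split.

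Finally, the SAP does not write pooled variance, and it names R without a function or variance option. R's standard t-test function uses Welch by default, so the analysis might already be run that way. That would remove the statistical problem, but the code would then differ from the test named in the text, which is itself a reason to settle the wording.

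**Conclusion.** The point holds in conditional form, as a cheap improvement. If the section 13 groups differ in both size and spread, within the assumed ranges (60 to 240 of 1,200; SD ratio 0.5 to 2; normal data), Student's type I error runs from about 0% to 29%. Wilcoxon's, read as a comparison of means, runs from about 0.3% to 13%. Welch stays near 5%.

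A reader might infer that the reported p-values will be wrong, or that the very unequal group sizes are enough to spoil them. The documents support neither. They give no split and no SDs, and unequal size with equal spread leaves both tests at about 5%.

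The consequences are limited. The primary analyses (SAP section 10) are event counts and ratios. The main secondary analyses (SAP section 11) are a survival ratio, Kaplan-Meier curves and Cox models. None uses a t-test or Wilcoxon.

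**What to change.** In SAP section 8, replace Student's t-test by Welch's t-test with a 95% confidence interval for the mean difference, chosen without a preliminary test of variances. Unequal variance then no longer triggers a switch of test. Keep Wilcoxon for strongly skewed variables, presented with medians and quartiles and labelled as a test of equal distributions.

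The cost is one sentence in the SAP and no new data. There are two downsides: Welch loses a little efficiency when variances are equal, and it is somewhat liberal for strongly skewed data with a small group (about 6–8% in the runs above). The second is the reason to keep Wilcoxon as the test for such variables.
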